IMPACT 2W Ki67	% PEPI 0	RFS (events)
$>10\%$	0/32 (0%)	9/35 (26%)
$\leq 10\%$	21/101 (21%)	13/118 (11%)
P Value	$P=0.004$ (Fisher)	$P=0.008$ (log rank)

In this trial, to avoid futile therapy, we plan to obtain tumor biopsy post 2 weeks of PD 0332991 in combination with anastrozole. Patients whose Day 15 Ki67 $>10\%$ will be considered resistant to the combination therapy. These patients will be recommended alternative therapies such as immediate surgery or neoadjuvant chemotherapy. The pre-PD 0332991 Ki67 will not be used for clinical decision making since PD 0332991 will be added to the treatment regimen. It is, however, important to obtain the pre-PD 0332991 Ki67 since this allows a comparison between anastrozole alone and the combination of anastrozole and PD 0332991 on the degree of Ki67 suppression.

1.9.2 To Assess Tumor Cell Apoptosis on Biopsies Taken Pre-PD 0332991 and Cycle 1 Day 15

We will investigate whether there is an increase in tumor cell apoptosis with the combination of PD 0332991 and anastrozole (or anastrozole in combination with goserelin). Anastrozole 1mg daily dosing reduced estradiol level by 70% by 24 hours and by approximately 80% after 14 days of daily dosing [AstraZeneca, Package Insert], therefore, full estrogen deprivation is expected by 28 days of anastrozole administration. In the case of goserelin, serum estradiol is suppressed to levels similar to those observed in postmenopausal women within 3 weeks

following administration. In addition, only 5% or less of women treated with goserelin, FSH and LH may not be suppressed to follicular phase levels on day 28 post treatment with a single 3.6mg depot injection [AstraZeneca, Package Insert].

1.9.3 To Assess the Degree of Ki67 Suppression before (Pre-PD 0332991) and after PD 0332991 (Cycle 1 Day 15)

The degree of Ki67 suppression following 2-4 weeks of therapy has been associated with the effectiveness of endocrine agents or the combination of endocrine agent with an mTOR inhibitor. In the IMPACT trial, suppression of Ki67 after 2 and 12 weeks was significantly greater with anastrozole than with tamoxifen ($P = 0.004$) which mirrored the result based on RFS in the ATAC trial [100]. These data indicate that Ki67 response early on therapy could potentially be employed as a measurement of treatment efficacy.

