1.9.4 To Assess Effect of PD 0332991 on Markers of Tumor Cell Senescence

Studies in preclinical models of ER+ breast cancer indicated that PD 0332991 induced stable cell cycle arrest that was fundamentally distinct from those elicited by ER antagonists and was capable of inducing aspects of cellular senescence, as measured by expression of senescence-associated b-galactosidase [20]. In addition, candidate proteins important for senescence including p16, IL6, cyclin D1, activated mTOR (such as pS6), FOXM1 phosphorylation, will be examined [19, 101]. These markers will be assayed on tumors collected at all time points. Since surgery occurs after at least 3 weeks after the last dose of PD 0332991, a comparison of these markers as well as Ki67 level between surgery and C1D15 sample will be informative in determining whether 4 months of combination therapy induced irreversible cell cycle arrest and cells have entered senescence.

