2.0 OBJECTIVES

Since surgery occurs 3 to 5 weeks following the last dose of PD 0332991 in order to avoid complications related to PD 0332991-induced myelosuppression, we propose to assess the primary endpoint of complete cell cycle arrest (Ki67 \leq 2.7%) on C1D15 while patients are receiving PD 0332991. The value of Ki67 on C1D15 and at surgery will provide data on the potential reversibility of Ki67 decrease when off PD 0332991 for at least 3 weeks. These data may help to hypothesize regarding the duration of the biologic effect of PD 0332991.

Amendment #5:

Please note that as of Amendment #5, a fifth cycle of daily PD 0332991 (consisting of 10-12 days of treatment, plus continued daily anastrozole) is added prior to surgery based on preliminary analysis of the first 18 patients showing an increase in tumor Ki67 at the time of surgery which was performed 3 to 5 weeks after the last dose of PD 0332991 (Cycle 4 Day 21). This data indicates that PD 0332991 has a reversible effect on cell cycle arrest. However, alternative explanations exist—for example, the emergence of resistance clones. To investigate these possibilities, we propose to re-initiate PD 0332991 (and continue anastrozole) for patients whose blood counts and other AEs recover sufficiently after 4 complete neoadjuvant cycles of PD 0332991 + anastrozole, and treat for an additional 10 to 12 days, with the last dose of PD 0332991 and anastrozole being administered on the day before surgery. Based on previous phase I studies, the mean ANC within 10-12 days of treatment is between 2.2 k-4.2 k/mcL (personal communication with Pfizer), therefore we expect majority of our patients will be able to complete Cycle 5. In fact, a neoadjuvant study consisting of 14 days of aromatase inhibitor +/- PD 0332991 before surgery is ongoing, and none of the first 9 patients randomized to receive PD 0332991 had ANC < 1,000 on Day 10 (personal communication with Pfizer).

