Adverse Events: All eligible patients that have initiated treatment will be considered evaluable for assessing adverse event rate(s). The maximum grade for each type of adverse event will be recorded for each patient using the NCI-CTCAE v4.0, and frequency tables will be reviewed to determine patterns. Additionally, the relationship of the adverse event(s) to the study treatment will be taken into consideration.

Ki67 suppression on Cycle 1 Day 1, Cycle 1 Day 15 and surgery: Following the approach of Dowsett et al. [26], the percent change in the Ki67 level from baseline will be determined on the log scale. A 95% t-confidence interval for the mean percent change in the Ki67 level from baseline will be constructed (if appropriate). The rate of complete cell cycle arrest on C1D1, C1D15, and surgery will be described by contingency tables compared by McNemar tests. Using trajectory analysis, we will also assess the association between distinct patterns of Ki67 change over time and clinical outcomes. Specifically, trajectory groups will be formulated to describe clusters of individuals with similar temporal patterns of Ki67 over time using finite mixture models with SAS procedure TRAJ. This method enables identification of the number of discrete trajectory types, and characterization of the shape and estimation of the prevalence of each type. We will choose the best models based on statistical tests (including Bayesian and Akaike information criterion, each of which test goodness-of-fit) and clinical judgment.

To assess the long term outcomes of patients treated in this trial: The long-term outcomes (i.e., pathologic complete response (pCr), local and distant recurrence, etc, as defined in section 12.4) will also be assessed in the PIK3CA wild and mutnt cohorts (separately and combined) and the endocrine resistant cohort, respectively. The categorical outcome will be summarized using contingency tables and compared by Fisher's exact test, while the time-to-event outcomes will be described using Kaplan-Meier product limit estimators and compared by log-rank test.

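### Section 15.5 plans no paired analysis of continuous Ki67 between C1D1 and C1D15 or between C1D15 and surgery, so the first lacks an effect estimate with an interval and the second relies on a low-power test in small groups

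*Combined protocol and SAP*

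**What the plan says.** Section 15.5 gives Ki67 three analyses:

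- Following an earlier study, "the percent change in the Ki67 level from baseline will be determined on the log scale", with a 95% t-interval for the mean change.
- "The rate of complete cell cycle arrest on C1D1, C1D15, and surgery will be described by contingency tables compared by McNemar tests".
- Trajectory groups, by which "we will also assess the association between distinct patterns of Ki67 change over time and clinical outcomes".

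No significance level, version of McNemar, SD, correlation or power is given for any change between visits.

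Other sections describe the same comparisons on the continuous scale. Section 1.9.1 says the biopsy before PD 0332991 "allows a comparison between anastrozole alone and the combination of anastrozole and PD 0332991 on the degree of Ki67 suppression". Section 1.9.4 says "a comparison of these markers as well as Ki67 level between surgery and C1D15 sample will be informative". Section 2.0 says "The value of Ki67 on C1D15 and at surgery will provide data on the potential reversibility of Ki67 decrease when off PD 0332991".

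In Section 2.2, objective 3 compares arrest rates at C1D1 and C1D15, and objective 4 concerns the Ki67 level at four time points. Section 9.3.2 reports Ki67 as a continuous value. Section 15.6 assigns repeated-measures ANOVA to estradiol, RB phosphorylation, senescence markers and drug concentrations, but not to Ki67.

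**The concern.** Two within-woman comparisons carry the biological argument: what PD 0332991 adds to anastrozole (C1D1 to C1D15), and whether suppression lasts (C1D15 to surgery). Neither has a planned estimate on the scale on which the protocol describes it. Separate intervals for change from baseline at each visit do not give an interval for the difference between visits, because the within-woman covariance is lost. The trajectory model relates patterns to outcome and does not estimate either contrast.

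McNemar counts only women who cross 2.7%. A rise that stays on one side of the cut adds nothing. In a small group, a non-significant table could be read as durable arrest when it mainly reflects few discordant pairs. Section 15.5 analyses cohorts separately by default, so small groups are the usual case.

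**Working it through.** **The plan's own figures.** No power is stated for these contrasts, so there is nothing to reproduce on this point. The wild type design does reproduce: with at least 20 of 33 required, the exact binomial gives alpha 0.041 at 44% and power 0.80 at 66%. It is unaffected.

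**C1D1 to C1D15, combined initial cohorts (Section 1.8).** Arrest at C1D15 was 39 of 45, and 26 women gained arrest after C1D1. Losses can be at most 45 − 39 = 6. Exact McNemar gives p = 3×10⁻⁸ for 26 v 0 and about 0.0005 for 26 v 6. The test is settled; the size of the Ki67 change is not estimated.

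**C1D15 to surgery: one scenario in full.** Inputs from the documents are arrest of 87% at C1D15 (Section 1.8) and 18 women, the size of the look reported under Amendment 5 (Section 2.0). Assumed are normal ln Ki67 with equal SD at both visits, within-woman correlation ρ of 0.3 to 0.7, a fall in arrest to 66%, and two-sided 5%.

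1. Shift in SD units: Φ⁻¹(0.87) − Φ⁻¹(0.66) = 1.126 − 0.412 = 0.714.
2. SD of the paired difference: √(2(1 − ρ)) = 1.183 at ρ = 0.3 and 0.775 at ρ = 0.7.
3. Standardised effect: 0.714/1.183 = 0.603 and 0.714/0.775 = 0.922. Multiplying by √18 gives noncentrality 2.56 and 3.91. Noncentral t on 17 df gives power of about 68% and 96%.
4. Discordant probabilities from the bivariate normal: loss 0.271 and gain 0.061 at ρ = 0.3; loss 0.233 and gain 0.023 at ρ = 0.7. Expected discordant pairs: 18 × 0.332 = 6.0 and 18 × 0.256 = 4.6.
5. Exact McNemar needs at least 6 discordant pairs, all one way: 2 × 0.5⁶ = 0.031, whereas 2 × 0.5⁵ = 0.0625. Power is 17% at either correlation. Uncorrected chi-square McNemar gives 34% and 46%.
6. Flooring values at 1% before the paired t gives about 51-79% at an SD of 1.25, or 47-84% over SDs of 1.0 to 1.5.

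**Where McNemar is weak and where it is adequate.** A second calculation fixed C1D15 arrest at the reported rate and assumed fold rises, SD 1.0-1.5 and correlation 0.3-0.6:

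| Group | Rise | Exact McNemar | Paired t, no floor |
|---|---|---|---|
| n=18, 87% arrested | 2-fold | 0.04-0.16 | 0.35-0.87 |
| n=18, 87% | 3-fold | 0.18-0.62 | 0.70-1.00 |
| Wild type n=28, 79% | 2-fold | 0.18-0.54 | 0.51-0.98 |
| Combined n=45, 87% | 3-fold | 0.67-0.99 | 0.98-1.00 |

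If half of the arrested women lose arrest and none gain it, exact McNemar has power 0.87 even at n=18.

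**Selection at C1D15.** Section 9.3.1 takes women with C1D15 Ki67 above 10% off study drug, so on-protocol surgery pairs are selected on a low first value. I simulated no true change with 25 women kept at 10% or below, SD 1.0-1.5 and correlation 0.3-0.7. With 20% arrested before selection (the endocrine-resistant alternative), the geometric mean ratio of surgery to C1D15 is about 1.2 to 2.3, and the paired t is significant in about 17-70% of trials. At 87% arrested, as in the initial cohorts, it is significant in about 5-6%.

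**The case against.** The best defence is that the trial is about arrest rates. The primary endpoint is the C1D15 rate, objective 3 is worded as a rate comparison that McNemar answers, and Section 2.0 presents the surgery data only as helping to form hypotheses. This stands, and it keeps the point to secondary analyses.

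A reader might infer that the whole C1D1 to C1D15 comparison is underpowered. The 26 conversions rule that out for the pooled test. A reader might also infer that a rebound will pass unseen. Section 2.0 already reports a rise at surgery in the first 18 women and concludes that the effect is reversible, so the remaining question is how large the rise is and in whom.

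The power gap is also not fixed. The plan does not say exact McNemar, the SD and correlation are not in the documents, and a floor narrows the gap.

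The strongest objection is to replacing McNemar with a single pooled paired t test. Under Sections 5.1 and 5.2, women who receive Cycle 5 have surgery on Day 11, 12 or 13 of that cycle, with the last PD 0332991 dose the day before; the others have it 3 to 5 weeks after their last dose. A pooled ratio would mix these groups and would not measure reversibility. In the endocrine-resistant cohort, selection alone can produce an apparent rise. Both objections hold and shape the fix.

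Changes from baseline can be subtracted for a point estimate when the same women contribute; only the interval is lost. In the endocrine-resistant cohort Section 9.1.3 schedules no sample before endocrine therapy, although diagnostic material may be requested to complete pairs.

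**Conclusion.** The gap in Section 15.5 is real: neither between-visit Ki67 change has a planned paired estimate with an interval. For C1D1 to C1D15 in the combined cohorts, the loss is the effect estimate, not power. For C1D15 to surgery, McNemar has low power for modest rises in small groups: 17% exact or 34-46% chi-square in the 18-woman scenario, against about 68-96% for the paired t, or about 51-79% with a 1% floor. It is adequate for a large rebound in the combined cohorts.

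These figures rest on ln-normal values, an assumed correlation of 0.3-0.7 and, for the floor, an assumed SD. The documents do not support the stronger readings that McNemar is the wrong test or that a paired t test should replace it throughout. The primary endpoint is untouched. The change is worth making because it is cheap and uses values already collected.

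**What to change.** In Section 15.5:

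- Add paired within-woman changes in ln Ki67 for C1D1 to C1D15 and for C1D15 to surgery, as geometric mean ratios with 95% intervals. Use the paired t, or Wilcoxon with Hodges-Lehmann if values are skewed or floored, and state the floor for zero values.
- Keep McNemar for the arrest rates.
- Report C1D15 to surgery separately for women on PD 0332991 at surgery (Cycle 5) and women 3 to 5 weeks off it. Use only the off-drug group for reversibility.
- In the endocrine-resistant cohort, label the C1D15 to surgery ratio descriptive and give the reason: retention on drug is selected on C1D15 Ki67 of 10% or less.
- In that cohort, show separately the C1D1 to C1D15 pairs in which the qualifying biopsy above 10% stands in for C1D1 (Section 10.2, note W), because regression to the mean affects them too.

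The cost is plan wording, a stated floor and a little more analysis. No new samples or patients are needed.

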12.4 Post-surgery

Local recurrence is defined as histologic evidence of ductal carcinoma in situ or invasive breast cancer in the ipsilateral breast or chest wall.

Regional recurrence is defined as the cytologic or histologic evidence of disease in the ipsilateral internal mammary, ipsilateral supraclavicular, ipsilateral infraclavicular and/or ipsilateral axillary nodes or soft tissue of the ipsilateral axilla.

Distant recurrence is defined as the cytologic, histologic, and/or radiographic evidence of disease in the skin, subcutaneous tissue, lymph nodes (other than local or regional metastasis), lung, bone marrow, central nervous system or histologic and/or radiographic evidence of skeletal or liver metastasis.

Second primary breast cancer is defined histologic evidence of ductal carcinoma in situ or invasive breast cancer in the contralateral breast or chest wall.

Second primary cancer (non-breast) is defined as any non-breast second primary cancer other than squamous or basal cell carcinoma of the skin, melanoma in situ, or carcinoma in situ of the cervix is to be reported and should be confirmed histologically whenever possible.

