15.5 Data Analysis

All data analyses will be performed separately for each cohort unless otherwise specified.

Demographic and clinical characteristics of the sample, as well as response, toxicity by grade, and loss to follow-up will be summarized using descriptive statistics. The rate of complete cell cycle arrest will be calculated and the corresponding 90% confidence interval (CI) will be provided. The rates for pCR and PEPI 0 and their 90% CIs will also be calculated. The differences in overall survival (OS) and relapse-free survival (RFS) for patients with or without complete cell cycle arrest on C1D1 will be described using Kaplan-Meier product limit estimator and compared by log-rank tests. Similar analysis will be performed for complete cell cycle arrest on C1D15 or patients with or without PEPI 0, with the two cohorts combined or separately. A trajectory analysis (see below) will also be performed for this comparison.

Analysis of other secondary endpoints:

Clinical response rate: The clinical response rate will be estimated by the number of patients whose disease meets the WHO criteria of complete or partial response prior to surgery divided by the total number of eligible patients who began combination neoadjuvant treatment. A 90% confidence interval for the true clinical response rate will be calculated using the Duffy-Santner approach for the endocrine resistant cohort (2-stage design). The complete cell cycle arrest rates and the corresponding 90% confidence intervals will also be calculated for PIK3CA wild type and mutant cohorts separately and combined.

Radiological response rate: The radiological response rate will be estimated by the number of patients whose disease meets with WHO criteria for complete or partial response at the evaluation prior to surgery divided by the total number of eligible patients who began

combination neo-adjuvant therapy. A 90% confidence interval for the true radiographic response rate will be calculated using the Duffy-Santner approach. The analysis will be performed with the two cohorts separately and combined.

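### Section 15.5 gives no competing-risks method: where Kaplan-Meier is applied to a single section 12.4 outcome, it will modestly overstate that outcome's first-event incidence

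*Combined protocol and SAP*

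**What the plan says.** Section 15.5 sets the scope of the long-term analysis: "The long-term outcomes (i.e., pathologic complete response (pCr), local and distant recurrence, etc, as defined in section 12.4) will also be assessed". It then splits the methods. For one group, "The categorical outcome will be summarized using contingency tables and compared by Fisher's exact test"; for the other, "the time-to-event outcomes will be described using Kaplan-Meier product limit estimators and compared by log-rank test". It does not say which outcomes fall in which group.

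OS and RFS have their own Kaplan-Meier and log-rank sentence earlier in section 15.5, which begins "The differences in overall survival (OS) and relapse-free survival (RFS) for patients with or without complete cell cycle arrest on C1D1".

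Section 12.4 defines five separate outcomes: local recurrence, regional recurrence, distant recurrence, second primary breast cancer and second primary non-breast cancer. For example: "Local recurrence is defined as histologic evidence of ductal carcinoma in situ or invasive breast cancer in the ipsilateral breast or chest wall". It gives no composite, no rule for the order of events, no time origin and no censoring rule. Neither competing risks nor cumulative incidence is mentioned anywhere in section 15.

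Follow-up is 5 years or until recurrence, whichever is earlier, in the postoperative schema, section 1.8, section 5.7 and footnote F of the section 10.3 calendar. Section 5.8 and footnote C of the section 10.2 calendar give 5 years without that limit.

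**The concern.** Recurrence over 5 years is naturally a time-to-event outcome. Since OS and RFS are already covered by their own sentence, the natural reading of the long-term paragraph is that Kaplan-Meier will be used for individual types of recurrence.

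For one type, the other types and death are competing events. A woman whose first event is distant recurrence generally stops being followed, and a woman who dies cannot recur. A component-wise Kaplan-Meier curve would by default censor both, and would treat them as if they kept the same future risk as the women still under observation. The quantity 1-KM is then no longer the probability that this event occurs first, and the component risks add to more than the risk of having any of them.

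Long-term outcome is secondary objective 10 in section 2.2. At stake is a correct description of how often each type of failure occurs, not the primary conclusion.

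**Working it through.** The plan states no event rate, power or sample size for the long-term outcomes, so it has no figure to reproduce. The size of the bias has to be shown under assumed rates.

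**Inputs from the documents.** The time horizon is 5 years (sections 1.8 and 5.7). Fifty women were enrolled in the PIK3CA cohorts (section 1.8). The endocrine resistant cohort has 37 women if both stages are completed (section 15.3).

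**Assumed inputs.** Hazards are constant. The 5-year first-event probabilities (locoregional, distant, second breast, other cancer, death) are:
- moderate risk: 4%, 12%, 2%, 4%, 3% (total 25%)
- higher risk: 8%, 25%, 2%, 4%, 4% (total 43%)

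Local and regional recurrence are merged here for brevity.

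**Formulas.** For a true cumulative incidence CIF_k and total P, the cumulative hazard is H_k = (CIF_k / P) × (−ln(1 − P)). A component Kaplan-Meier curve then gives 1-KM_k = 1 − exp(−H_k).

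**Moderate risk.** −ln(0.75) = 0.2877.
- Locoregional: H = (4/25) × 0.2877 = 0.0460, so 1-KM = 4.5% against 4%.
- Distant: H = (12/25) × 0.2877 = 0.1381, so 1-KM = 12.9% against 12%.

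**Higher risk.** −ln(0.57) = 0.5621.
- Locoregional: H = (8/43) × 0.5621 = 0.1046, so 1-KM = 9.9% against 8%.
- Distant: H = (25/43) × 0.5621 = 0.3268, so 1-KM = 27.9% against 25%.

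**Sum of the components, leaving out death because it is not a section 12.4 outcome.**

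| Scenario | Locoregional | Distant | Second breast | Other cancer | Sum of 1-KM | True sum |
|---|---|---|---|---|---|---|
| Moderate | 4.5% | 12.9% | 2.3% | 4.5% | 24.2% | 22% |
| Higher | 9.9% | 27.9% | 2.6% | 5.1% | 45.5% | 39% |

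**Sensitivity to second primaries.** Only recurrence is said to end follow-up, so a recurrence after a second cancer could still be seen. With the same hazards and only recurrence and death competing, the true incidence is (H_k / ΣH) × (1 − exp(−ΣH)).
- Moderate: ΣH = 0.0460 + 0.1381 + 0.0345 = 0.2186. Locoregional incidence is 4.1%, against 1-KM of 4.5%.
- Higher: ΣH = 0.1046 + 0.3268 + 0.0523 = 0.4837. Locoregional incidence is 8.3%, against 1-KM of 9.9%.

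**A second set of assumptions.** Let the total be 10%, 25% or 40%, split 50% distant, 20% local or regional, 15% second primary and 15% death. Over the non-death components the overstatement is 0.1 to 2.5 percentage points, or 3% to 23% in relative terms.

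**Comparison with sampling error,** √(p(1 − p)/n):
- p = 4%, n = 50: standard error 2.8 points, bias 0.5 points.
- p = 12%, n = 50: standard error 4.6 points, bias 0.9 points.
- p = 8%, n = 37: standard error 4.5 points, bias 1.9 points.
- p = 25%, n = 37: standard error 7.1 points, bias 2.9 points.

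**The case against.** The strongest reply is that section 15.5 does not promise these curves. It divides outcomes into categorical and time-to-event without assigning any section 12.4 outcome to either group, and the only endpoints it explicitly sends to Kaplan-Meier are OS and RFS. The type of recurrence might simply be tabulated. That is a possible reading, and it is why the point is conditional. It does not remove the need for a change: a Fisher's exact test on recurrence counts would ignore unequal follow-up and would handle competing deaths no better.

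A reader might also infer that every section 12.4 outcome, second cancers included, will be estimated by Kaplan-Meier and that every component risk will be overstated. The documents do not support that:
- Second cancers are not named in section 15.5. They enter only through "local and distant recurrence, etc, as defined in section 12.4".
- No censoring rule is written. Censoring at competing events is the default of a component-wise curve, not a stated choice.
- Second primaries are not said to end follow-up, so they compete only if a first-event definition is adopted.
- If no competing event comes first, 1-KM and cumulative incidence agree.

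The log-rank comparison is not itself an error, since it validly tests cause-specific hazards. Finally, the bias is smaller than the sampling error, and no decision rule depends on it. That stands, and it sets the severity. It does not make the estimator right: the bias always runs upward, and pooling the cohorts would not remove it.

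**Conclusion.** The point holds in a conditional form and is minor. If Kaplan-Meier is applied to a single section 12.4 outcome, with women censored at another type of recurrence or at death, 1-KM overstates its first-event incidence. Under the assumed 5-year totals of 25% and 43%, the excess is 0.5 and 1.9 percentage points for locoregional recurrence and 0.9 and 2.9 points for distant recurrence. Locoregional recurrence is the more distorted in relative terms (9.9% against 8% is about 24%) and distant recurrence in absolute terms.

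These sizes rest on assumed rates, constant hazards and second primaries counted as competing first events. If second primaries do not compete, the locoregional excess falls to about 0.4 and 1.6 points (4.5 − 4.1 and 9.9 − 8.3). The direction of the bias needs only that some competing events come first. The primary endpoint is not involved, and this bias does not affect OS or an RFS that counts any relapse or death as an event.

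**What to change.** Amend the long-term outcomes paragraph of section 15.5 as follows:

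1. Keep Kaplan-Meier and log-rank for OS and RFS.
2. State which section 12.4 outcomes are analysed as time-to-event and which are only tabulated.
3. For each time-to-event component, list the competing events: at least the other types of recurrence and death, with second primaries added only if a first-event definition is adopted.
4. Estimate single components by the Aalen-Johansen cumulative incidence function.
5. Compare groups by Gray's test, or keep the log-rank test and label it a comparison of cause-specific hazards.

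The cost is one paragraph of SAP text and standard software. No new data are needed.
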